5.2. Specification of Baseline Values

The baseline value is the last observed data recorded prior or equal to the first dose date of study drug.

For vital signs parameters, measures that are taken at the latest time prior to drug administration will be defined as baseline values.

For MRI, baseline values are those taken up to 14 days following first dose of study drug.

For ECG, the mean value for 3 pre-dose assessments will define the baseline value. Worst case scenario will be used for character values.

5.3. Multiple Comparisons and Multiplicity

The overall significant level for this study is 5%, using two-tailed tests and/or two-sided confidence intervals with 95% confidence level. In order to protect the study from type-I error inflation, the secondary endpoints will be interpreted inferentially only if a statistically significant treatment effect is detected in the primary analysis. Type-I error will be further controlled by employing the Hierarchical Approach, (i.e. each secondary endpoint will be analyzed only in case the preceding endpoint will have a p-value less or equal to 0.05) according to the following order:

1. Time to CDP as measured by EDSS

2. Time to CDP event as measured by EDSS or T25FW
3. Change from baseline to week 48 in the T25FW test
4. The number of new T2 lesions at week 48

5.4. Definition of Country/Geographical Region (CGR)

Country will be added as a covariate in all analyses. All centers within a country will be pooled. Out of all countries participating in the study, there may be some countries with low number of patients in the ITT population. These countries may be pooled with neighboring countries or countries having similar standard of care to form larger geographical regions. Details of such pooling will be discussed and documented in SDR prior to revealing the blind.

5.5. Handling Withdrawals and Missing Data

If a patient performs an early termination (ET) visit, then this ET visit will be considered as next scheduled visit for the summaries and analyses of the following items: MRI data (following week 36 only), T25FW, 9HPT, EDSS, SDMT, CVLT (following week 24 only), BVMT (following week 24 only), LCVA and MSWS-12. Listings will present early termination visit records as they appear in the data.

The total EDSS score is composed of eight functional system scores (FSS). If any of the FSS are missing at a particular time point, the total EDSS score will also be considered missing at that time point.

Missing dates will be imputed as follows for data related to PPMS history (see Section 6.3):

1. In cases where only day is missing/unknown, then the 1st of the month will be imputed.
2. In cases where both day and month are missing/unknown, then the 1st of January will be imputed.
3. In cases where the whole date is missing, the date will be considered as missing.
4. In listings, dates will appear as they are in the data (i.e., missing/unknown values as “UNK”).

The MSWS-12 score will be calculated as the sum of the 12 items of the questionnaire. In case there are one or two items missing, the mean of the non-missing items per patient will be imputed. In a case with more than 3 items missing, the total score will be considered missing as well. Listings will present the item data as appears in the data.

Following CDP related endpoints definition (see Section 7.4.1), a CDP cannot be confirmed during a protocol defined relapse, whereas relapse occurrence is identified by relapse onset and approximate stabilization date. If a relapse onset is partial then assessment date of the relapse will be used instead. If a relapse stabilization date is partial, then the last day of the relevant month will be used in that date. Similar imputation of relapse onset and stabilization dates will be done for definition of protocol defined relapses (see Section 7.5.18) if needed. Listings will present relapse related information as appears in the data.

For all other variables, only the observed data from the patients up to study completion or study withdrawal will be used in the statistical analyses, i.e., there is no plan to impute missing data for other variables.

5.6. Study days and visit windows

Study days will be numbered relative to the 1st day of study drug administration. The start of treatment (day 1) is defined as the date on which a patient takes the 1st dose of study drug. Days will be numbered relative to study start (i.e., ..., -2, -1, 1, 2, ...; with day 1 being the start of study drug and day -1 being the day before the start of study drug). No windows schemes will be applied to the data.

For by-visit summaries, if there are multiple assessments at a post baseline time point then the last non-missing assessment at that visit will be used for the summary.

6. STUDY POPULATION

6.1. General

The ITT population will be used for all study population summaries unless otherwise noted. Summaries will be presented by treatment group, and overall, unless otherwise noted.

6.2. Patient Disposition

Patients screened, patients screened but not in the ITT population, and the reason the patients were not in the ITT population will be summarized only for all patients using patient counts. Patients in the ITT population, patients in the ITT population who were not treated, patients in the safety population, mITT1, mITT2, PP population, patients who completed part A of the study, patients who completed part B of the study, patients who performed an ET visit during part A, and patients who performed an ET visit during part B will be summarized using descriptive statistics. Patients who perform an ET visit during part A or part B will also be summarized using descriptive statistics by reason for ET. In addition, patients who performed an ET visit during part A or part B, but continue to come for follow-up visits will be presented as well. Patients who completed part A of the study will be defined as patients who did not perform an early termination visit prior to the database lock of part A of the study. This summary will include all patients screened into the study. The denominator for calculating the percentages will be the number of patients in the ITT population.

In addition, the distribution of ITT patients by county, and by country and site will be summarized using descriptive statistics.

6.3. Demographics and Baseline Characteristics

Demographics and baseline characteristics will be presented for the following populations: ITT, mITT1, patients who performed an ET visit during part A of the study, patients who completed part A of the study, patients who performed an ET visit during part B of the study, patients who completed part B of the study.

Patient demographics and baseline characteristics will be examined to assess the comparability of the treatment groups. The continuous variables of patient age, weight, height, and body mass index (BMI), will be summarized using descriptive statistics. The categorical variables of patient sex, race and ethnicity will be summarized using descriptive statistics for each category. Missing categories will be presented if necessary.

Baseline PPMS characteristics will be presented in a separate table. Continuous variables of time from 1st MS symptom (years) to informed consent, time from PPMS diagnosis (years) to informed consent, EDSS will be summarized using descriptive statistics. The categorical variables of previous use of disease modifying treatments, combination of tests used to meet PPMS criteria (at least two), patients with positive CSF, areas with evidence of clinical disability progression in the 2 years prior to screening, EDSS raw score and EDSS score defined as ≤ 4.5 and >4.5 will be summarized using descriptive statistics for each category. Missing categories will be presented if necessary.

Baseline MRI measurements will be presented in a separate table as well. Continuous variables of normalized brain volume, T2 lesion volume, and number of T1 enhancing lesions will be summarized using descriptive statistics. The categorical variable of patients with T1 enhancing lesions at baseline will be summarized using descriptive statistics for each category

Tobacco usage will also be summarized using descriptive statistics.

The following statistical tests will be incorporated for baseline tabulations between 0.6mg and placebo:

- Analysis of variance (ANOVA) with treatment group and CGR as factors will be used for all continuous variables presented for demography, PPMS history and normalized brain volume.
- Wilcoxon-Mann-Whitney test will be used for EDSS and for T2 lesion volume.
- Cochran-Mantel-Haenszel (CMH) test, stratified by CGR will be used for all categorical variables.

6.4. Medical History

All medical history will be coded using the Medical Dictionary for Regulatory Activities (MedDRA). Patients with at least 1 abnormal medical history finding and abnormal findings for each system organ class and preferred term will be summarized using descriptive statistics.

Patients are counted only once in each system organ class, and only once in each preferred term category.

6.5. Prior Medications

All prior medications will be coded using the World Health Organization dictionary of medical codes (WHO Drug). The incidence of prior medications use will be summarized using descriptive statistics by therapeutic class and preferred term. Patients are counted only once in each therapeutic class category, and only once in each preferred term category. Prior medications will include all medications taken prior to the first day of study drug treatment.

6.6. MS Disease Modifying Treatment History

All treatments will be coded using WHO Drug. The incidence of treatments will be summarized using descriptive statistics by therapeutic class and preferred term. Patients are counted only once in each therapeutic class category, and only once in each preferred term category.

6.7. Electrocardiogram

Electrocardiogram findings at baseline based on investigator interpretation (normal, abnormal not clinically significant, abnormal clinically significant, and missing) and based on ERT interpretation (normal, abnormal and unable to evaluate) will be summarized using descriptive statistics. The denominator for calculating percentages of patients with scans for each category will be a number of patients with available electrocardiogram scans at baseline.

6.8. Protocol Violations

Patients with at least 1 protocol violation as recorded on the CRF for each category will be summarized using descriptive statistics.

When the study is completed, the table of protocol violations will be generated again to include both part A and part B.

7. EFFICACY ANALYSIS

7.1. General

The mITT1 or mITT2 populations will be used for all efficacy analyses unless otherwise noted. Summaries will be presented by treatment group.

7.2. Primary Efficacy Variable and Analysis

The primary efficacy variable for this study is BA as measured by the PBVC from baseline to week 48. This endpoint will be analyzed using the mITT1 population and will include all the assessments done up to one month after the last dose of the study drug (all the following assessments will be excluded from this analysis). BA will be analyzed using baseline-adjusted repeated measures analysis of covariance (ANCOVA- SAS® PROC MIXED) in which 1 contrast will be constructed in order to compare between laquinimod 0.6 mg and placebo.

The model will be comprised from the treatment group as a class variable (2 levels). In addition to the treatment group, week (categorical, 2 levels), treatment by week interaction, normalized brain volume at baseline, natural logarithm of T2 lesion volume at baseline, and CGR will be used as covariates. Additionally, week (categorical) will be specified as a repeated effect and unstructured (UN) correlation matrix will be used to model intra-subject correlation. In case a convergence issue will arise using the UN correlation matrix, (1) AR1 or (2) Compound Symmetry (CS) will be used to enable model convergence (in this order). The SAS code for this analysis is as follows:

```
PROC MIXED;
  CLASS SUBJID ARM WEEK CGR;
  MODEL BA=ARM WEEK ARM*WEEK NBVBASE LT2BASE CGR / SOLUTION CL;
  REPEATED WEEK / TYPE=UN SUBJECT=SUBJID R RCORR;
  ESTIMATE 'Laq 0.6 to Plb on Week 48' ARM 1 -1 ARM*WEEK 0 1 0 -1 / CL;
  LSMEANS ARM*WEEK / PDIFF CL;
  WHERE ARM in ('Laquinimod 0.6 mg', 'Placebo');
RUN;
```

In addition, mean values of the BA as measured by the PBVC from baseline to weeks 24 and 48 will be summarized using descriptive statistics.

Since for the purpose of this analysis scans of patients who discontinue the study after week 36 are considered as scans at week 48 (see Section 5.5), PBVC measures from the scans of these patients will be presented also separately using descriptive statistics.

The assumption of a no treatment-by-covariate interaction will be evaluated by a separate repeated measures ANCOVA model (SAS® PROC MIXED) with the items treatment, week (categorical), week by treatment interaction, CGR, baseline covariate, and treatment-by-baseline covariate interaction included in the model. If there is evidence of treatment-by-covariate interaction ($p \leq 0.10$), further exploration of this interaction will be done graphically/descriptively and the treatment p-values will still be reported from the main effects model (repeated measures ANCOVA from above).

The consistency of treatment effects among different CGR will be evaluated by a separate repeated measures ANCOVA model (SAS® PROC MIXED) with treatment, week (categorical), and week by treatment interaction, CGR, and treatment-by-CGR interaction in the model. If there is evidence of a treatment-by-CGR interaction ($p \leq 0.10$), a descriptive summary of treatment differences for each CGR will be used to identify the Country (or Countries) for which the treatment effects are consistent with the remaining countries. This will be an exploratory analysis and the treatment p-values will still be reported from the main effects model (repeated measures ANCOVA from above).

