## 4. SELECTION AND WITHDRAWAL OF PATIENTS

### 4.1. Patient Inclusion Criteria

Patients may be included in the study only if they meet all of the following criteria:

1. Patients must have a confirmed and documented PPMS diagnosis as defined by the 2010 Revised McDonald criteria (see [Appendix D](#)).
2. Baseline MRI showing lesions consistent with PPMS in either or both brain and spinal cord.
3. Patients must have an EDSS score of 3 to 6.5, inclusive, at both screening and baseline visits.a
4. Documented evidence of clinical disability progression in the 2 years prior to screening.
5. FSS of  $\geq 2$  for the pyramidal system or gait impairment due to lower extremity dysfunction.
6. Patients must be between 25 to 55 years of age, inclusive.
7. Women of child-bearing potential (for example women who are not postmenopausal or surgically sterilized) must practice an acceptable method of birth control for 30 days before taking the study drug, and 2 acceptable methods of birth control during all study duration and until 30 days after the last dose of treatment is administered. Acceptable methods of birth control in this study include: intrauterine devices, barrier methods (condom or diaphragm with spermicide), and hormonal methods of birth control (eg, oral contraceptive, contraceptive patch, long-acting injectable contraceptive).
8. Patients must sign and date a written informed consent prior to entering the study.
9. Patients must be willing and able to comply with the protocol requirements for the duration of the study.

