### 6.4.1. MRI Evaluations

The patients will undergo up to 3 MRI scans:

- baseline (at least 14 days but not more than 6 weeks prior to baseline)
- week 24
- week 48 (or ET visit if performed after the week 36 visit and prior to week 48).

Gd will be administered at baseline MRI only. In case of steroid treatment, study MRI should be performed before or be delayed to allow a minimum of 14 days, but not more than 28 days, from the completion of the steroid course.

The following parameters will be assessed:

- normalized brain volume - at baseline
- PBVC – at week 24 as well as week 48 or ET
- T2-lesions volume – at baseline, as well as week 48 or ET
- T1 hypointense lesions volume - at baseline, as well as week 48 or ET
- number of GdE-T1 lesions – at baseline
- number of new T2 lesions - at week 48 or ET
- number of new T1 hypointense lesions - at week 48 or ET
- thalamic volume, cortical volume, and white matter volume - at baseline
- percent volume change (thalamus, cortex, white matter) - at week 48 or ET
- normalized cervical cord area based on 3D T1-w acquisition of the cervical cord - at baseline
- cervical cord area percentage volume change - at week 48 or ET
- number of T2 cervical cord lesions based on a sagittal T2 acquisition of the cervical cord - at baseline
- number of new T2 cervical cord lesions based on a sagittal T2 acquisition of the cervical cord - at week 48 or ET
- normal-appearing brain tissue average MTR, at baseline, as well as week 48 or ET

If MTR is not performed due to MRI site technical limitations, this would not be considered a protocol violation.

Additional details of MRI procedures are presented in [Appendix F](#) and in the MRI manual.

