#### **2010 McDonald criteria for diagnosis of MS in disease with progression from onset**

PPMS may be diagnosed in patients with:
1. One year of disease progression (retrospectively or prospectively determined)
2. Plus 2 of the 3 following criteria a :
A. Evidence for DIS in the brain based on $\geq 1$ T2 b lesions in at least 1 area characteristic for MS (periventricular, juxtacortical, or infratentorial)
B. Evidence for DIS in the spinal cord based on $\geq 2$ T2 b lesions in the cord.
C. Positive CSF (isoelectric focusing evidence of oligoclonal bands and/or elevated immunoglobulin G index).

a If a patient has a brainstem or spinal cord syndrome, all symptomatic lesions are excluded from the criteria.

b Gadolinium enhancement of lesions is not required

MS = multiple sclerosis; PPMS = primary progressive MS; DIS = lesion dissemination in space; CSF = cerebrospinal fluid; IgG = immunoglobulin G

Note: In this study, if criterion C (positive CSF) is applied toward the diagnosis of PPMS, the CRF documentation must be accompanied by source documentation of the results issued by the clinical laboratory which performed the analysis.

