MRI scans are evaluated locally for any incidental pathology (ie, pathology unrelated to, or inconsistent with, the patient's known MS) according to locally determined procedures. If such pathology is found, the Treating Neurologist should be notified. The MRI reading center will evaluate the scans for the purposes of performing quantitative measurements and confirming Inclusion Criteria #2 (Lesions consistent with PPMS in either or both brain MRI and cervical spinal cord MRI). In order not to compromise blinding of the study, the MRI Reading Center will not report MRI findings back to the clinical site.

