Time to CDP as measured by EDSS confirmed after at least 12 weeks will be analyzed using the ITT population and will include data from all the study assessments done up to seven days after the last dose of the study drug (all the following assessments will be excluded from this analysis). This analysis will be performed using a baseline adjusted Cox's proportional hazards regression model (SAS® PROC PHREG) in which 1 contrast for comparing laquinimod 0.6 mg to placebo will be constructed. In addition to treatment group, categorical EDSS at baseline (≤ 4.5 or > 4.5), age at baseline, natural logarithm of T2 lesion volume at baseline, and CGR will be used as covariates. The SAS code for this analysis is as follows:

```

PROC PHREG;
  CLASS ARM EDSSBASE CGR;
  MODEL TIME_TO_PROGRESSION*CENSOR(1,2,3)=ARM EDSSBASE AGE LT2BASE CGR / COVB RL;
  CONTRAST 'Laq 0.6 to Plb' ARM 1 / ESTIMATE=EXP;
  WHERE ARM in ('Laquinimod 0.6 mg', 'Placebo');
RUN;

```

In case the above model will not converge due to CGR variable, then CGR will be removed from the model.

The adequacy of the proportional hazards assumption will be confirmed by including a time-dependent covariate of laquinimod 0.6 mg (as dummy variables) by log (time) interaction in the analysis model and testing it at the 5% level. In case the proportional hazards assumption will

be rejected, the log rank test (SAS® PROC LIFTEST) will be used for statistical inference. The SAS code for checking the proportional hazards assumption is as follows:

```
PROC PHREG;
  CLASS ARM EDSSBASE CGR;
  MODEL TIME_TO_PROGRESSION*CENSOR(1,2,3)=ARM ARMT EDSSBASE AGE LT2BASE CGR ;
    ARMT = ARM*log(TIME_TO_PROGRESSION);
    PROP_HAZARDS_TEST_LAQ_0_6: test ARMT;
    WHERE ARM in ('Laquinimod 0.6 mg', 'Placebo');
  RUN;
```

In case the above model will not converge due to CGR variable, then CGR will be removed from the model.

In addition, patients with CDP will be summarized using descriptive statistics. The time to CDP will be presented by Kaplan-Meier curves stratified by treatment group.

EDSS scores and changes from baseline to each visit will be summarized using descriptive statistics.

All analyses presented in the section will be repeated to include both part A and part B when the study is completed.

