7.4.2. Time to CDP event as measured by EDSS or T25FW

Time to CDP as measured by EDSS or T25FW will be defined by reaching at least 1 of the following 2 types of event for each individual:

- An increase from baseline in EDSS score (≥ 1 point from baseline EDSS, if EDSS at entry is ≤ 5.0 or increase of ≥ 0.5 point, if EDSS at entry is ≥ 5.5), confirmed after at least 12 weeks, **or**
- An increase of at least 20% from baseline in the T25FW test, confirmed after at least 12 weeks

Progression cannot be confirmed during a protocol defined relapse. A similar algorithm to that described for CDP as measured by EDSS will be used for definition and censoring rules of this variable (see Section 7.4.1).

T25FW will be calculated as a mean time of two T25FW trials at each visit. In cases when a patient could not complete a T25FW trial due to the physical limitations a value of 180 seconds will be assigned for that trial (this is the maximal possible value for the T25FW test).

Time to CDP as measured by EDSS or T25FW, confirmed after at least 12 weeks will be analyzed using the ITT population and will include data from all the study assessments done up to seven days after the date of last dose of the study drug (all the following assessments will be excluded from this analysis). This analysis will be performed using baseline adjusted Cox's proportional hazards regression model (SAS® PROC PHREG) in which 1 contrast for comparing laquinimod 0.6 mg to placebo will be constructed. In addition to treatment group, categorical EDSS at baseline (≤ 4.5 or > 4.5), age at baseline, T25FW at baseline, natural logarithm of T2 lesion volume at baseline, and CGR will be used as covariates. The SAS code for this analysis is as follows:

```

PROC PHREG;
  CLASS ARM EDSSBASE CGR;
  MODEL TIME_TO_PROGRESSION*CENSOR(1,2,3)=ARM EDSSBASE T25BASE AGE LT2BASE CGR /
COVB RL;
  CONTRAST 'Laq 0.6 to Plb' ARM 1 / ESTIMATE=EXP;
  WHERE ARM in ('Laquinimod 0.6 mg', 'Placebo'); RUN;

```

In case the above model will not converge due to CGR variable, then CGR will be removed from the model.

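### Does logging baseline T2 lesion volume, with no rule for a zero, undermine four of the five endpoints in the testing hierarchy?

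*SAP*

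**What the plan says.** SAP 5.3 makes the primary endpoint a gatekeeper and then orders four secondary endpoints, so that "each secondary endpoint will be analyzed only in case the preceding endpoint will have a p-value less or equal to 0.05". The natural log of baseline T2 lesion volume (LT2BASE in the code) enters these models:

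- SAP 7.2, PBVC, mITT1 population: "normalized brain volume at baseline, natural logarithm of T2 lesion volume at baseline, and CGR will be used as covariates".
- SAP 7.4.1, time to CDP by EDSS, ITT population: "natural logarithm of T2 lesion volume at baseline, and CGR will be used as covariates".
- SAP 7.4.2, time to CDP by EDSS or T25FW, ITT population: "T25FW at baseline, natural logarithm of T2 lesion volume at baseline, and CGR will be used as covariates".
- SAP 7.4.4, number of new T2 lesions, mITT1 population: the same covariate, with age and CGR.

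The T25FW change model in SAP 7.4.3 does not use it. The by-gender versions of the four models above (SAP 7.5.21) carry it over.

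On eligibility, Protocol 4.1 requires "Baseline MRI showing lesions consistent with PPMS in either or both brain and spinal cord", and Appendix F has the reading center confirm "Lesions consistent with PPMS in either or both brain MRI and cervical spinal cord MRI". Appendix D asks for one year of progression "Plus 2 of the 3 following criteria", one of which is cord lesions and another a positive CSF. Protocol 6.4.1 records T2 lesion volume and, as a separate item, the "number of T2 cervical cord lesions based on a sagittal T2 acquisition of the cervical cord - at baseline".

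SAP 5.5 lists specific imputations. T2 volume is not among them, and no other imputation is planned.

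**The concern.** A patient diagnosed on cord lesions plus positive CSF need not have brain lesions in the areas that the criteria name. Cord lesions are counted but given no volume, so the logged variable, read as a brain measure, could be zero. SAS returns a missing value for the log of zero, and PROC MIXED, PHREG and GENMOD leave out records with a missing covariate. The patient would still be counted in ITT or mITT1 but would not contribute to the fit.

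The SAP's contingency rules do not catch this. They cover failure to converge (other covariance structures, or removal of CGR from the Cox models), and a missing covariate causes no such failure. The log-rank test that replaces the Cox model when proportional hazards is rejected has no covariates, so it would bring the patient back, and the set analysed for CDP would depend on that test.

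At stake would be the fits behind the primary p-value and three of the four secondary p-values, two of them labelled ITT.

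**Working it through.** **Count of affected models.** One primary plus four secondaries makes five endpoints. PBVC, both CDP endpoints and new T2 lesions use the logged volume; T25FW change does not. Four of five is correct.

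**Can a zero occur?** The eligibility text permits it but does not imply it. Cord plus CSF is one of three ways to meet two of three criteria. A patient who enters that way may still have brain T2 lesions outside the criterion areas, and those have volume. Only a volume of exactly zero breaks the log. The documents give no count of such patients.

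**The plan's own power figure.** Inputs from Protocol 9.2: difference 0.3, SD 0.8, two-sided 5%, 126 evaluable per arm.

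Power = Φ(0.3 / (0.8·√(2/n)) − 1.96) = Φ(0.375·√(n/2) − 1.96)

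At n = 126: 0.375·√63 = 2.976, and Φ(1.016) = 84.5%. The two-sample t calculation gives 84.3%. The stated 84% is reproduced. Inflating for 10% dropout, 252/0.9 = 280.

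**Loss of precision for PBVC.** The share with zero volume is assumed and taken as equal in the two arms.

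| Assumed share | Lost of 252 | n per arm | Power |
|---|---|---|---|
| 0% | 0 | 126 | 84.5% |
| 1% | 2.5 | 124.7 | 84.2% |
| 3% | 7.6 | 122.2 | 83.4% |
| 5% | 12.6 | 119.7 | 82.7% |
| 10% | 25.2 | 113.4 | 80.6% |

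On the t scale, 5% takes 84.3% to 82.4%. Power first falls below 80% at 112 per arm (79.8%), which is 14 lost per arm, or 14/126 = 11%.

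**Loss of precision for CDP.** If events fall in proportion to patients, the SE of the log hazard ratio grows by 1/√(1 − share): 1.005 at 1% and 1.026 at 5%. The documents state no power for CDP. Taking 80% as a reference, 5% gives Φ(2.802·√0.95 − 1.96) = Φ(0.771) = 78.0%.

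**Bias.** Baseline volume is measured before treatment, so leaving out patients on that value does not depend on arm. A simulation of 4,000 runs (126 per arm, ANCOVA at one visit, true difference 0.30, 5% zeros, an assumed lognormal volume) gave mean estimates of 0.302 with zeros deleted and 0.301 with ln(1 + volume). The SEs were 0.1010 and 0.0984, a ratio of 1.026, which is just 1/√0.95. It adds little beyond the assumed 5% loss, and its inputs are not in the documents.

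**Would a zero be seen?** SAP 6.3 summarises baseline T2 volume, SAP 5.1 includes the number and minimum in those statistics, and Tables 15.6.1 and 15.6.2 present it for ITT and mITT1. SAP 6.3 also tabulates the combination of tests used for diagnosis. None of this information needs the treatment code, and SAP 4.5 and 5.4 already provide for a data review before the blind is broken.

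**Would the patient disappear from the report?** For PBVC, the analysis without covariates in SAP 7.3 retains the patient. For CDP, the event summaries and Kaplan-Meier curves on ITT do so, though without inference.

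**The case for a change.** The best case for a change is that the covariate sits in the gatekeeping test and most of what follows it, that one sentence would settle the matter, and that without it a programmer who meets a zero must choose between deleting, flooring and adding a constant. Made after unblinding, that choice would be discretionary in the primary model. For CDP, deletion would also contradict a population defined as all randomized patients.

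The factual parts stand: the count of models, the eligibility route, the absence of a rule and the default SAS behaviour. Three things weaken the conclusion.

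- The population definitions point the analyst one way. ITT and mITT1 include the patient, and a volume of zero is an observed value, so giving it a usable number is a derivation and does not breach the rule against imputing missing data.
- It cannot be said that the number of patients in each fit goes unreported. SAP section 13 lists table titles only, and no table shells are in the file.
- The obvious remedy, ln(1 + volume) throughout, alters a prespecified covariate for every patient to accommodate a group that may be empty. It also depends on a unit that the documents do not give. In the simulation, moving the constant from 0.01 to 1 shifted the estimate by 0.007 on average, against an SE of about 0.099.

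The exploratory models in SAP 7.5.6 and 7.5.7 log the baseline volume and then rank it. For positive volumes the ranks are the same with or without the log, so only a zero would be affected, and these analyses lie outside the hierarchy.

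**Conclusion.** No change is needed. The SAP leaves one derivation unwritten, for a value that eligibility permits and the documents do not show to occur. Followed exactly as written, with any such patients dropped, the analysis would still give an unbiased comparison. It would lose under 2 points of PBVC power at an assumed 5% share and about 4 points (84.5% to 80.6%) at an assumed 10%. An analyst who met a zero would see it in the baseline MRI data and keep the patient, as the population definitions require. The conclusion rests on two assumptions: that zeros are rare, and that they fall evenly across arms, as randomization makes likely. The first is not verifiable from the documents, but even a share well above the 1% to 5% range would leave the primary test close to its planned power.
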